9.3.2.1. General safety events

General safety events (which will be assessed using a SCRI design) are listed along with their risk interval definitions in [Table 5](#). Event-specific risk intervals have been defined to reflect a period of potentially increased risk following vaccination. Event-specific control intervals will be defined in a pre-specified period (to be specified in the SAP) following the risk interval. Buffer and control intervals for each outcome will be defined to reflect the baseline risk of the outcome and will take into consideration the duration of the risk interval, the potential seasonality of the outcome, and the recommended timing between the initial bivalent vaccine dose and additional COVID-19 vaccine doses.

Table 5. General safety events

Organ system	Safety event of interest	Risk interval (days following vaccination [Day 0])	Ages to be included in analyses ^a
Cardiac	Myocarditis/pericarditis	1-7	Ages ≥ 6 months
	Acute myocardial infarction	1-28	Ages ≥ 6 months
Neurologic	Acute disseminated encephalomyelitis	1-42	Ages ≥ 6 months
	Bell's palsy	1-42	Ages ≥ 6 months
	Convulsions	1-42	6 months through 4 years
	Encephalomyelitis/encephalitis	1-42	Ages ≥ 6 months
	Guillain-Barré syndrome	1-42	Ages ≥ 6 months
	Transverse myelitis	1-42	Ages ≥ 6 months
Hematologic	Deep vein thrombosis	1-28	Ages ≥ 6 months
	Disseminated intravascular coagulation	1-28	Ages ≥ 6 months
	Immune hemolytic anemia	1-42	Ages ≥ 6 months
	Immune thrombocytopenia	1-42	Ages ≥ 6 months
	Pulmonary embolism	1-28	Ages ≥ 6 months
	Thromboembolic events associated with thrombocytopenia	1-28	Ages ≥ 6 months

090177e19f732934\Approved\Approved On: 14-Dec-2023 13:35 (GMT)

PFIZER CONFIDENTIAL

Table 5. General safety events

Organ system	Safety event of interest	Risk interval (days following vaccination [Day 0])	Ages to be included in analyses ^a
	Thrombotic thrombocytopenic purpura	1-28	Ages ≥ 6 months
	Venous thromboembolism	1-28	Ages ≥ 6 months
	Hemorrhagic stroke	1-28	Ages ≥ 6 months
	Ischemic stroke	1-28	Ages ≥ 6 months
Respiratory	Acute respiratory distress syndrome	1-28	Ages ≥ 6 months
Other system	Anaphylaxis	0-1	Ages ≥ 6 months
	Appendicitis	1-42	Ages ≥ 6 months
	Kawasaki disease	1-42	Ages 6 months through 4 years
	Multisystem inflammatory syndrome	1-42	Ages ≥ 6 months
	Multisystem inflammatory syndrome in children	1-42	Ages < 21 years

COVID-19 = coronavirus disease 2019.

a. Subgroup analysis will also be performed among pregnant women, immunocompromised individuals, individuals with a recorded history of severe COVID-19, and in subgroups defined by age, and for myocarditis/pericarditis, by subgroups defined jointly by age and sex; additional subgroup analysis may be performed by vaccine formulation and receipt of the bivalent vaccine as a primary series vs booster dose if feasible in the data sources. See Sections 9.7.4 and 9.7.5 for further details.

090177e19f732934\Approved\Approved On: 14-Dec-2023 13:35 (GMT)

9.3.2.2. Pregnancy and birth outcomes

Pregnancy outcomes and birth outcomes, including clinical definitions, method for identification in the data sources, and the period at risk are provided in Table 6.

Table 6. Pregnancy outcomes and birth outcomes

Outcome type	Safety event of interest	Clinical definition and method for identification in the data sources	Period at risk
Pregnancy outcomes	Spontaneous abortion	Defined as spontaneous pregnancy loss before 20 completed weeks of gestation; to be identified via diagnosis codes	From pregnancy start until 19 weeks and 6 days of gestation
	Stillbirth	Defined as spontaneous pregnancy loss on or after 20 completed weeks of gestation; to be identified via diagnosis codes	From 20 weeks of gestation until pregnancy end
	Preterm birth	Defined as live birth before 37 completed weeks of gestation; to be identified via diagnosis codes	< 37 weeks of gestation
Birth outcomes	Major congenital malformations	Defined a major defect as a congenital abnormality that requires medical or surgical treatment, has a serious adverse effect on health and development, or has significant cosmetic impact (NBDPN, 2021); to be identified in live-born infants using diagnosis codes based on the National Birth Defects Prevention Network case definitions (NBDPN, 2023)	First trimester of pregnancy ^a
	Small size for gestational age	Defined as less than 10 th percentile of weight for gestational age; to be identified using diagnosis codes for small size for gestational age or combinations of diagnosis codes for birthweight (in categories) and gestational age (in categories)	Any time during pregnancy ^a

a. Although the etiologic period for major congenital malformations is the first trimester and for small size for gestational age is any time during pregnancy, these events can only be reliably observed in infants after birth.

9.3.3. Covariates

Table 7 presents variables that will be used for descriptive analysis in analyses of general safety events as well as variables that will be used for descriptive analysis, matching, and

090177e19f732934\Approved\Approved On: 14-Dec-2023 13:35 (GMT)

propensity score estimation in analysis of pregnancy and birth outcomes. These variables will be identified using claims or electronic health records data (where available).

Table 7. Covariates used for descriptive analysis, matching or propensity score estimation

Variable	General safety events	Pregnancy and birth outcomes		
	Descriptive	Descriptive	Matching	Propensity scores
Age (as of the index date or LMP ^a)	X	X	X	
Sex	X			
Geographic region (based on the most recent information at the time of data refresh)	X	X	X	
Immunocompromising conditions (in the 12 months before the index date) 
 Including immunodeficiencies, immunosuppressant medication use, HIV and other immunosuppressing conditions, and receipt of organ or bone marrow transplants 	X	X		X
Pregnancy status as of the index date	X			
History of severe COVID-19 disease (as of the index date) 
 Defined with inpatient diagnoses in the principal diagnosis position or in pregnant women, with inpatient claims with a principal diagnosis of viral diseases complicating pregnancy and a diagnosis of COVID-19 in another position 	X	X		X
Receipt of the index Pfizer-BioNTech COVID-19 bivalent Vaccine as a primary series dose vs booster dose; only to be assessed if feasible to identify in the data sources; anticipated to be incomplete	X	X		
Other vaccines recommended for routine use (on the index date or from 28 days before pregnancy until end of pregnancy) ^b	X	X		X
Estimated pregnancy start date (LMP)		X	X	
Gestational age on the index date ^c		X		

090177e19f732934\Approved\Approved On: 14-Dec-2023 13:35 (GMT)

Table 7. Covariates used for descriptive analysis, matching or propensity score estimation

Variable	General safety events	Pregnancy and birth outcomes		
	Descriptive	Descriptive	Matching	Propensity scores
Comorbidities (in the 12 months before the index date); separate variables for the following conditions: 
 • History of anaphylaxis • History of vaccine-related allergies • Diabetes (type 1 and type 2) • Hypertension • Cardiovascular disease • Cerebrovascular diseases • Chronic respiratory disease • Chronic kidney disease • Chronic liver disease • Cancer • Epilepsy • Infections • Connective tissue disorders • Thyroid disorders • Mood disorders • Asthma • Obesity (capture anticipated to be incomplete in the data sources) 		X		X
Healthcare utilization in the 12 months before or on the index date		X		X
Alcohol abuse and smoking in the 12 months before or on the index date (capture anticipated to be incomplete)		X		X
Reproductive history (in all data available before the index date; if feasible in the data sources): 
 • Spontaneous abortions in previous pregnancies • Pregnancy terminations in previous pregnancies 		X		X
Pregnancy complications during the current pregnancy ^d : 
 • Multiple pregnancy • Gestational diabetes • Preeclampsia/eclampsia • TORCH infections 		X		X
Teratogenic medications (from 28 days before pregnancy start until end of pregnancy ^d)		X		X

090177e19f732934\Approved\Approved On: 14-Dec-2023 13:35 (GMT)

Table 7. Covariates used for descriptive analysis, matching or propensity score estimation

Variable	General safety events	Pregnancy and birth outcomes		
	Descriptive	Descriptive	Matching	Propensity scores

COVID-19 = coronavirus disease 2019; LMP = date of last menstrual period; TORCH = toxoplasmosis, other (syphilis, varicella-zoster, parvovirus B19), rubella, cytomegalovirus, and herpes infections.

a. To be assessed on the index date for general safety events and on LMP for pregnancy and birth outcomes.

b. To be assessed on the index date for analysis of general safety events and from 28 days before LMP until end of pregnancy for pregnancy and birth outcomes. Only information up to and including the index date will be included in propensity scores.

c. Applies only to pregnancy outcomes analysis.

d. Except for multiple pregnancy, only information up to and including the index date will be included in propensity scores.

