- Neurologic: acute disseminated encephalomyelitis, Bell's palsy, convulsions (in children aged 6 months to 4 years), encephalomyelitis/encephalitis, Guillain-Barré syndrome, transverse myelitis
- Hematologic: deep vein thrombosis, disseminated intravascular coagulation, immune hemolytic anemia, immune thrombocytopenia, pulmonary embolism, thromboembolic events associated with thrombocytopenia, thrombotic thrombocytopenic purpura, venous thromboembolism, hemorrhagic stroke, ischemic stroke
- Respiratory: acute respiratory distress syndrome
- Other system: anaphylaxis, appendicitis, Kawasaki disease (in children aged 6 months to years), multisystem inflammatory syndrome; multisystem inflammatory syndrome in children (in individuals aged < 21 years)

The following pregnancy and birth outcomes will be assessed in pregnant women or their infants:

- Spontaneous abortion (spontaneous pregnancy loss before 20 completed weeks of gestation)

PFIZER CONFIDENTIAL

CT24-WI-GL02-RF02 4.0 Non-Interventional Study Protocol Template For Secondary Data Collection Study

01-Jun-2022

Page 14 of 62

- Stillbirth (fetal deaths at or after 20 completed weeks of gestation)
- Preterm birth (live birth before 37 completed weeks of gestation)
- Major congenital malformations
- Small size for gestational age

Vaccine exposures

Receipt of Pfizer-BioNTech bivalent COVID-19 Vaccine and other COVID-19 vaccines will be identified in claims and/or electronic health records data via pharmacy dispensing and/or procedure codes. In analyses of pregnant women, exposures occurring within 28 days before the estimated pregnancy start or during pregnancy will be considered. Where quality data from existing linkages with immunization registries are available for use in research studies, immunization registry data will also be used to identify receipt of COVID-19 vaccines.

Covariates

Covariates for analysis of general safety events will include demographics, immunocompromising conditions, pregnancy status, history of severe COVID-19, geographic region, whether vaccination with Pfizer-BioNTech COVID-19 bivalent Vaccine was for a primary or booster dose (if feasible), and formulation type of Pfizer-BioNTech COVID-19 Vaccine (ie, bivalent or multivalent vaccine if additional formulations of Pfizer-BioNTech COVID-19 are authorized during the study observation period) and receipt of other vaccines recommended for routine use on the index date.

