9.2.1. Study population eligibility criteria

9.2.1.1. Population to assess general safety events

Individuals will be eligible for analysis of general safety events (which will use an SCRI design) if they meet the following criteria:

1. Aged ≥ 6 months for at least 1 day during the study observation period.
2. Have received a dose of Pfizer-BioNTech bivalent COVID-19 Vaccine. Note that individuals will be eligible regardless of the brand(s) of any COVID-19 vaccines received before Pfizer-BioNTech bivalent COVID-19 Vaccine.
3. Have had continuous medical and pharmacy insurance coverage for at least 12 months before receipt of the Pfizer-BioNTech bivalent COVID-19 Vaccine, or from birth until receipt of the Pfizer-BioNTech bivalent COVID-19 Vaccine (for individuals aged younger than 12 months at the time of receipt of the vaccine). For children aged younger than 12 months at the time of vaccination, a delay in enrollment (duration to be specified in the SAP) from birth will be allowed.

Additionally, for analysis of each safety event, individuals will be required to meet the following criteria:

4. Have experienced the event of interest during the risk or control intervals (see Section 9.3.2.1 for event-specific risk interval definitions; event-specific control intervals will be defined in the SAP)
5. Did not experience the specific safety event of interest during the pre-event washout period (the event-specific washout periods will be defined in the SAP)
6. Have continuous health plan enrollment from the start of the event-specific risk interval until the end of the event-specific control interval (for individuals who live until the end of the control interval) or until death (for individuals who die before the end of the control interval)

7. Have received no additional doses of COVID-19 vaccine other than Pfizer-BioNTech bivalent COVID-19 Vaccine during the risk interval and no additional doses of COVID-19 vaccine of any brand through the end of the control interval. Additional doses of Pfizer-BioNTech bivalent COVID-19 Vaccine will be allowed during the risk interval to enable the capture of more than 1 dose administered in a short timeframe, as the vaccine is currently approved for use as more than 1 dose in the primary series.

The index date (ie, date of cohort entry) will be the date of receipt of Pfizer-BioNTech bivalent COVID-19 Vaccine.

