9.7.3.3. Confounding

Comparisons between vaccinated and unvaccinated pregnant women may be confounded, as unvaccinated women may differ substantially with respect to health-seeking behaviors and other risk factors for pregnancy and birth outcomes. For pregnancy and birth outcomes, a sensitivity analysis will be performed among pregnant women with a recorded history of monovalent COVID-19 vaccination before cohort entry, which may serve as a proxy for these health-seeking behaviors. This sensitivity analysis will also address potential misclassification of unexposed status, as women with a recorded history of monovalent COVID-19 vaccination may have more complete data on bivalent COVID-19 vaccination.

Confounding by time-invariant characteristics is not a concern in the SCRI design because it is self-controlled.

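### In the self-controlled analysis, no listed analysis separates the bivalent dose from another vaccine given on the same day, so the IRR is a joint effect for any event that the other vaccine influences

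*Protocol*

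**What the plan says.** The Abstract lists "receipt of other vaccines recommended for routine use on the index date" among the covariates for general safety events. Section 9.3.3 states their role: "Table 7 presents variables that will be used for descriptive analysis in analyses of general safety events". In Table 7 the row for other routine vaccines, "Other vaccines recommended for routine use (on the index date or from 28 days before pregnancy until end of pregnancy", is marked as descriptive for general safety events. For pregnancy and birth outcomes it is marked as descriptive and also for the propensity score. Footnote b gives the timing for the self-controlled design: "To be assessed on the index date for analysis of general safety events". Section 9.2.1.1 fixes that day: "The index date (ie, date of cohort entry) will be the date of receipt of Pfizer-BioNTech bivalent COVID-19 Vaccine".

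Eligibility criterion 7 in the same section limits other COVID-19 vaccine doses only ("Have received no additional doses of COVID-19 vaccine other than Pfizer-BioNTech bivalent COVID-19 Vaccine during the risk interval", and none of any brand from then to the end of the control interval). It does not address other vaccines.

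Table 5 starts the risk interval on Day 0 for anaphylaxis and on Day 1 for the other events, ending on Day 1, 7, 28 or 42. The control interval follows after a buffer. Section 9.7.1 specifies a conditional Poisson or similar model of risk against control interval and names no term for co-administration.

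On confounding in this design, Section 9.7.3.3 says "Confounding by time-invariant characteristics is not a concern in the SCRI design because it is self-controlled". Section 9.9 accepts that time-varying confounding is possible and relies on keeping each person's observation short. Section 9.7.5 closes with an optional provision for further subgroups by clinically relevant variables, none of them named.

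**The concern.** Self-matching removes whatever is constant within a person over the observation period. Another vaccine given on Day 0 is not constant: it switches on at the same moment as the bivalent dose. Within a co-vaccinated person the two exposures coincide completely, so the risk-versus-control contrast estimates their combined effect. Shortening the observation period helps against season and slow trends, but it cannot pull apart two exposures that begin on the same day.

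Primary objective 1 will be read as the relative risk associated with the bivalent vaccine. If a raised IRR appears for an event, the listed analyses offer no way to see whether it persists in people who received the bivalent dose alone. A null IRR has the mirror problem if a later effect of the other vaccine has raised the control-interval rate.

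**Working it through.** **1. Do the listed analyses separate co-administered doses?**

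- 9.7.1: risk against control interval only.
- 9.7.3: alternative risk intervals, exposure misclassification (pregnancy cohort), confounding (pregnancy cohort), outcome misclassification. None uses same-day vaccines.
- 9.7.4: pregnancy, immunocompromise, severe COVID-19 history, age, and sex by age for myocarditis/pericarditis. Same-day vaccines are not included.
- 9.7.5: primary series against booster if feasible, plus the optional unnamed subgroups.
- Table 10: summarises these analyses and lists nothing on co-administration.

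**2. Baseline figure.** Table 8 gives power 0.86 for 80 events, IRR 2.0, two-sided alpha 0.05 and equal intervals. The signed-root likelihood-ratio formula for self-controlled case series, with ρ = 2 and r = 0.5, gives:

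- A = 2[(ρr/(ρr+1−r))·ln ρ − ln(ρr+1−r)] = 2[0.6667 × 0.6931 − 0.4055] = 0.1133
- B = (ln²ρ/A)·ρr(1−r)/(ρr+1−r)² = (0.4805/0.1133) × 0.5/2.25 = 0.943
- Power = Φ[(√(80 × 0.1133) − 1.96)/√0.943] = Φ(1.08) = 0.860

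This agrees with the protocol. All 24 cells of Table 8 reproduce to within 0.005, so the power table is not in dispute.

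**3. Size of the bias.** Let q be the share of baseline events that occur in co-vaccinated people, and IRRco the other vaccine's rate ratio acting within the event's risk interval. With a true bivalent IRR of 1, the risk-interval rate relative to control is (1 − q) × 1 + q × IRRco, so

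apparent IRR = 1 + q(IRRco − 1).

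The protocol gives neither input. All values below are assumed.

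| q | IRRco 1.5 | IRRco 2 | IRRco 3 |
|---|---|---|---|
| 0.1 | 1.05 | 1.10 | 1.20 |
| 0.2 | 1.10 | 1.20 | 1.40 |
| 0.3 | 1.15 | 1.30 | 1.60 |
| 0.4 | 1.20 | 1.40 | 1.80 |

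With 80 events, the chance of declaring a raised IRR (nominal upper tail 2.5%) is 4.1% at an apparent IRR of 1.05, 12.5% at 1.20 and 21.3% at 1.30. At 1.80 it is 73%, from Table 8 itself.

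**4. Opposite direction.** If the other vaccine's effect fell across the control interval instead, the apparent IRR would be 1/[1 + q(IRRco − 1)]. For q = 0.2 and IRRco = 2 this is 1/1.20 = 0.83.

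**5. Cost of restriction.** If 20% of events are in co-vaccinated people, 80 × 0.8 = 64 remain. Power at IRR 2.0 is Φ[(√(64 × 0.1133) − 1.96)/√0.943] = 0.775. At 10% (72 events) it is 0.82, and at 30% (56 events) 0.72.

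**6. Precision of a comparison between strata.** With equal intervals and IRR near 1, the variance of log IRR is about 4/n. For 64 and 16 events, the standard error of the log ratio of IRRs is √(4/64 + 4/16) = 0.56. The 95% interval therefore runs from the estimate divided by 3.0 to the estimate multiplied by 3.0 (exp(1.96 × 0.559) = 2.99).

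**The case against.** The strongest reply is that the protocol records the variable, sends detailed methods to the SAP (not available here), and leaves room in 9.7.5 for further subgroups. A route to the analysis therefore exists. That is true, but the route is optional and unnamed, and a stratification chosen after a raised IRR has been seen would carry less weight than one fixed beforehand.

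Several stronger readings are tempting, and the protocol does not support them:

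- A reader might infer that marking the variable as descriptive rules out stratifying by it. It does not. That is the only column Table 7 gives this design, and age, immunocompromise, pregnancy status and severe COVID-19 history are marked the same way yet have subgroup IRRs in 9.7.4.
- A reader might infer that the other vaccine's effect must lie entirely in the risk interval. Table 5's windows are described as follows: "Event-specific risk intervals have been defined to reflect a period of potentially increased risk following vaccination". They are short for some events (Days 0 to 1, Days 1 to 7), and another vaccine's effect could come later, in the buffer or the control interval.
- A reader might infer that all 24 events in Table 5 are affected. Bias arises only where a co-administered vaccine changes the risk of that event, and the protocol does not say that any does.
- A reader might take the sentence in 9.7.3.3 as an error. It is correct for what it covers, and 9.9 acknowledges time-varying confounding.

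It is also fair that the size rests on two assumed inputs, and that q is a share of baseline events. This equals the share of people co-vaccinated only if both groups have the same baseline risk.

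**Conclusion.** The point holds as a gap in the listed analyses, not as a contradiction or a wrong figure. Following them as written yields a combined effect in co-vaccinated people, and the safeguards that the protocol cites do not address same-day exposure. The likely distortion is upward when the other vaccine acts within the event's risk interval and may be downward when it acts in the control interval. There is none for events that the other vaccine does not influence. The range of 1.05 to 1.80 for a true IRR of 1.0 is conditional on q of 0.1 to 0.4 and IRRco of 1.5 to 3, and its upper end needs both inputs at their highest assumed values. The change is worth making because the flag is already collected and attribution to the bivalent vaccine is how primary objective 1 will be read.

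**What to change.** Keep the overall IRR as the primary estimate. Add to Section 9.7.3 and Table 10 a pre-specified sensitivity analysis for each general safety event that reaches a minimum event count fixed in advance, restricted to bivalent doses with no other vaccine recorded on the index date. Report the co-administered stratum beside it, with a risk-interval-by-co-administration interaction estimate and its CI. Base statements about attribution on these results together, and do not switch from one IRR to another on an undefined judgement that they differ.

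The programming cost is modest: a further stratification of the existing query across the research partners. The statistical cost is fewer events and wider intervals. The 64 and 16 event example shows that the interaction will often be imprecise, so a wide interval must not be read as evidence that the strata agree. Other vaccines may also be incompletely captured, leaving some co-vaccinated people in the restricted set. The report should state this limitation.

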9.2.2. Pregnancy outcomes (spontaneous abortion, stillbirth, and preterm birth)

Separate cohorts of pregnant women exposed to Pfizer-BioNTech bivalent COVID-19 Vaccine (exposed cohort) and pregnant women not exposed to any COVID-19 vaccine (unexposed cohort) will be formed for the final analysis of pregnancy outcomes (Table 1). To be eligible for either cohort, pregnant women must be enrolled from 12 months before cohort entry (ie, the index date) until the end of pregnancy.

Table 1. Cohort definitions for analysis of pregnancy outcomes

Cohort	Eligibility criteria	Index date
Exposed cohort	
 Receipt of a dose of Pfizer-BioNTech bivalent COVID-19 Vaccine in the exposure window (as defined in Table 3) Continuous enrollment in the 12 months before the index date until end of pregnancy 	
 Date of vaccination
Unexposed cohort	
 No receipt of any COVID-19 vaccine in the exposure window (as defined in Table 3) Continuous enrollment in the 12 months before the index date until end of pregnancy Matched individually (in a ratio of at least 1:1) to exposed women on estimated pregnancy start (LMP, within pre-specified calendar intervals), maternal age, and US state (if feasible, or broader geographic region if not feasible) 	
 Equivalent of the gestational age at vaccination (in days) in the exposed match. For example, if an exposed individual was vaccinated at 28 weeks and 3 days of gestation, the index date for unexposed matches would be set to 28 weeks and 3 days after their LMP.

COVID-19 = coronavirus disease 2019; LMP = date of last menstrual period; US = United States.

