9.2.3. Birth outcomes (major congenital malformations and small size for gestational age)

Separate cohorts of pregnant women exposed to Pfizer-BioNTech bivalent COVID-19 Vaccine (exposed cohort) and pregnant women not exposed to any COVID-19 vaccine (unexposed cohort) will be formed for the analysis of birth outcomes (Table 2). To be eligible for either cohort, women must have had a singleton pregnancy ending in a livebirth and must have had continuous enrollment from 12 months before the index date until birth. The index date in both exposed and unexposed women will be the LMP date. Analyses will be limited to pregnant women whose singleton pregnancies have ended in a livebirth and who have been successfully linked to an infant.

Table 2. Cohort definitions for analysis of birth outcomes

Cohort	Eligibility criteria
Exposed cohort	
 Pregnancy ending in a livebirth, with continuous enrollment in the 12 months before the index date (LMP) until birth Pregnancy linked to at least 1 infant Receipt of Pfizer-BioNTech bivalent COVID-19 Vaccine during the outcome-specific exposure window (as defined in Table 3)
Unexposed cohort	
 Pregnancy ending in a livebirth, with continuous enrollment in the 12 months before the index date (LMP) until birth Pregnancy linked to at least 1 infant

PFIZER CONFIDENTIAL

Table 2. Cohort definitions for analysis of birth outcomes

Cohort	Eligibility criteria
	
 No receipt of any COVID-19 vaccine during the outcome-specific exposure window (as defined in Table 3) Matched individually (in a ratio of at least 1:1) to exposed women on LMP, maternal age, and US state (if feasible, or broader geographic region if not feasible)

COVID-19 = coronavirus disease 2019; LMP = date of last menstrual period. US = United States

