9.2.3.1. Exposure windows for analyses in pregnant women

Outcome-specific exposure windows are provided in Table 3. For pregnancy and birth outcomes, only women who were exposed to Pfizer-BioNTech bivalent COVID-19 Vaccine during outcome-specific exposure windows will be eligible for the exposed cohorts. For each pregnancy and birth outcome, the exposure window will be from 28 days before pregnancy start until the end of the outcome-specific risk period (as defined in [Section 9.3.2.2](#)).

Table 3. Exposure windows for analysis of pregnancy outcomes and birth outcomes

Type of safety event	Safety event of interest	Exposure window
Pregnancy outcomes	Spontaneous abortion	From 28 days before LMP until 19 weeks and 6 days of gestation
	Stillbirth	From 28 days before LMP until pregnancy end
	Preterm birth	From 28 days before LMP until 36 weeks and 6 days of gestation
Birth outcomes	Major congenital malformations	From 28 days before LMP until the last day of the first trimester
	Small size for gestational age	From 28 days before LMP until pregnancy end

LMP = date of last menstrual period.

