9.3. Variables

9.3.1. Vaccine exposures

Receipt of Pfizer-BioNTech bivalent COVID-19 Vaccine and other COVID-19 vaccines will be identified in claims and/or electronic health records data via pharmacy dispensing and/or procedure codes. Where quality data from existing linkages with immunization registries are available for use in research studies, immunization registry data will also be used to identify receipt of COVID-19 vaccines.

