9.7.2. Analysis of pregnancy and birth outcomes

Among pregnant women, the distribution of demographics, comorbidities, and other potential confounders will be reported and compared between the matched exposed and unexposed cohorts. Covariate balance in the matched and weighted cohorts will be assessed using standardized differences or other suitable methods.

Vaccinated pregnant women will be matched to pregnant unexposed comparators in a ratio of exposed:unexposed of at least 1:1 on maternal age, US state (if feasible, or broader geographic region if not feasible), and pregnancy start (to address confounding by calendar time). Confounding by other variables will be addressed using inverse probability of treatment weighting, based on propensity scores estimated in the matched population.

In each data RP, measures of incidence or prevalence of pregnancy and birth outcomes and associated 95% CIs will be estimated within the matched exposed and unexposed cohorts.

Cox models or Poisson regression will be used to calculate adjusted HRs or incidence rate ratios and 95% CIs for spontaneous abortion, stillbirth, and preterm birth. For major congenital malformations and small size for gestational age, logistic regression will be used to estimate PORs and 95% CIs.

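### For the three pregnancy outcomes, the propensity-score utilization window includes the index day, which only in exposed women can hold the vaccination record that defines exposure

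*Protocol*

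**What the plan says.** Protocol Section 9.3.3, Table 7, marks "Healthcare utilization in the 12 months before or on the index date" both for description and for propensity scores in the pregnancy and birth outcome analyses. The comorbidity row of the same table covers the 12 months before the index date and does not add the index date itself.

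For the pregnancy outcomes, Table 1 (Section 9.2.2) gives the exposed index date as "Date of vaccination" and the unexposed index date as "Equivalent of the gestational age at vaccination (in days) in the exposed match". Section 9.3.1 says that receipt of COVID-19 vaccines "will be identified in claims and/or electronic health records data via pharmacy dispensing and/or procedure codes", with immunization registry data added where linkages of adequate quality exist.

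For the birth outcomes, Section 9.2.3 says: "The index date in both exposed and unexposed women will be the LMP date". The exposure window in Table 3 for malformations is "From 28 days before LMP until the last day of the first trimester". For small size for gestational age it also opens 28 days before the LMP.

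Section 9.7.2 gives the score its role: "Confounding by other variables will be addressed using inverse probability of treatment weighting, based on propensity scores estimated in the matched population". The protocol does not say which contacts make up utilization, and nothing in it removes the index vaccination record from the count.

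**The concern.** A propensity-score covariate should describe a woman before exposure and be measured alike in both arms. Here the last day of the window is an encounter day by construction in one arm and a calculated day in the other. If the vaccination visit or dispensing counts as a contact, the covariate contains the exposure itself. Weighting then treats an exposed woman with k earlier contacts like an unexposed woman with k + 1.

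Section 9.7.3.3 says that unvaccinated women may differ substantially in health-seeking behavior. Utilization is one of the measured variables in Table 7 that bears on this, so an error in it can leave part of that confounding in place. The standardized differences planned in Section 9.7.2 would be computed on the same affected variable and would look acceptable.

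**Working it through.** The plan states no figure for this point, so there is none to reproduce. The check has three steps.

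**1. The window by arm and outcome**

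| Analysis | Exposed index day | Unexposed index day | Study-vaccine record inside the window? |
|---|---|---|---|
| Spontaneous abortion, stillbirth, preterm birth | vaccination date | assigned gestational day | Yes, on the index day, exposed only |
| Malformations, small size for gestational age | LMP | LMP | Only doses from 28 days before LMP through LMP |

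**2. What weighting does**

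Let U be true contacts before the index day, A exposure (1 or 0), and V = 1 if the vaccination record counts as a contact. The measured covariate is X = U + A·V. Weighting on X makes mean X about equal in the two arms. Hence

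weighted mean U (exposed) − weighted mean U (unexposed) ≈ −P(V = 1).

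If every record counts, the gap is about one contact; if half count, about half a contact.

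**3. Size under a true null.** All inputs are assumptions; the documents give none of them.

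*Model A.* 400,000 women; U is Poisson with a gamma(shape 4, scale 2) mean, so 8 contacts on average; P(exposed) = expit(−0.4 + 0.05U); outcome risk = 0.10·b^(U−8); logistic score on the count.

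- Window ended before the index day: risk ratio 1.00 for every b.
- Every vaccination record counted: true utilization differs by −1.08 contacts after weighting. The risk ratio is 0.989, 0.978 and 0.966 when risk rises 1%, 2% and 3% per contact, and 0.942 at 5%.
- Half of the records counted: the 3% case becomes 0.984.
- Risk falling 2% or 3% per contact, every record counted: 1.021 and 1.031.

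*Model B.* Gamma-Poisson counts with dispersion 2; score saturated on the count; outcome log risk ratio of +0.2 or −0.2 per SD of log(1 + count); exposure log-odds of 0 or 0.3 per SD. With the window ended before the index day the risk ratio is again 1.00 throughout. With the record counted:

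| Mean contacts | Records counted | RR, utilization raises risk | RR, utilization lowers risk | Residual gap in true utilization (SD) | Women in a non-overlap cell |
|---|---|---|---|---|---|
| 3 | half | 0.959–0.962 | 1.045–1.049 | −0.21 to −0.23 | 0% |
| 3 | all | 0.917–0.918 | 1.110–1.112 | −0.47 to −0.48 | 8–10% |
| 8 | half | 0.980–0.981 | 1.025–1.026 | −0.11 | 0% |
| 8 | all | 0.960 | 1.057 | −0.24 | 2–3% |
| 15 | half | 0.988–0.989 | 1.015–1.016 | −0.07 | 0% |
| 15 | all | 0.976 | 1.034–1.035 | −0.14 | about 1% |

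**Scale against sampling error.** Section 9.5.2 illustrates power with 20,000 women per group. Preterm birth at 10% gives 2,000 events per group and a log-scale 95% half-width of 1.96·√(2/2,000) = 0.062. Stillbirth at 0.5% gives 100 events per group and 1.96·√(2/100) = 0.28. A shift of 0.01 to 0.03 is a visible part of the first and negligible beside the second.

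**The case against.** The strongest reply is that the size rests on choices the protocol has not made. It does not define utilization. A count of inpatient or emergency contacts would leave out nearly all vaccination records, and a dose known only from a registry need not produce a claim. This stands, and it limits the point to measures that include outpatient, procedure or dispensing records. It does not remove the point, because the window itself is fixed in Table 7.

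Models A and B also adjust for utilization alone. Table 7 adds comorbidities, immunocompromising conditions and more. When risk was made to depend on latent morbidity (3% per unit) and a noisy comorbidity score was added, a bias of 0.978 shrank to between 0.983 and 0.995. That stands too.

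Four stronger readings are tempting and not supported:

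- A reader might infer that the hazard ratio is pulled below 1. The sign follows the utilization–outcome association, which the documents do not give. If more contacts mark health-seeking and lower risk, the ratio rises above 1.
- A reader might take 0.942 as the expected size and set it against the preterm half-width of 0.062, since ln(0.942) = −0.060. That case needs risk to rise 5% per contact, or 1.05^16 = 2.2-fold between 0 and 16 contacts, with every record counted. The 20,000 per group is a power illustration, not a planned size.
- A reader might infer that overlap fails. In Model A only about 1% of women have no contacts, (1/3)^4 = 1.2%. It reaches 8–10% only with a mean of 3 contacts and every record counted.
- A reader might extend the point to all five outcomes, or rank it as the main threat to validity. The birth-outcome index date is the LMP in both arms. Section 9.7.3.3 ranks no threat, and the proxy it names for health-seeking is prior monovalent vaccination, not utilization.

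The alcohol and smoking row, "Alcohol abuse and smoking in the 12 months before or on the index date (capture anticipated to be incomplete"), shares the window and gives exposed women an extra chance to be recorded. No figure supports an effect of any size there.

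**Conclusion.** The point holds for spontaneous abortion, stillbirth and preterm birth. As worded, Table 7 lets the record that defines exposure enter a confounder in the exposed arm only, and the planned balance checks cannot reveal it. With about 8 contacts a year, every record counted and a risk gradient of 1 to 3% per contact, a null risk ratio shifts by about 1 to 3%; the shift halves if half of the records count. With low counts and a strong association the range widens to about 0.92 to 1.11. The direction is unknown, and the effect is small or absent for inpatient or emergency counts and for registry-only doses. For malformations and small size for gestational age, only doses from 28 days before LMP through LMP are affected. This is a modest, avoidable bias in a stated window and should be corrected, but it does not undermine the design.

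**What to change.** In Table 7, for the pregnancy-outcome analyses, end the utilization window on the day before the index date in both arms, as the comorbidity row already does. Alternatively, keep the window and state that the index vaccination encounter and dispensing are not counted as utilization. For the birth outcomes, also exclude study-vaccine records from 28 days before LMP through LMP from the count; shortening the window by one day would not remove those.

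The cost is one covariate parameter or one exclusion rule, set before the final-analysis queries that Section 6 expects in the second quarter of 2026. Shortening the window loses genuine same-day contacts; the exclusion rule keeps those that are separate from the vaccination encounter. Changing the alcohol and smoking window is optional: its effect is not quantified, and it would drop some records of variables whose capture is already expected to be incomplete.
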